### **1.2 Study Design**

[figure not shown]
#### **1.2.1 Synopsis of Study Design**

This is an open-label, single-arm, multicenter study enrolling postmenopausal women with osteoporosis . The study is designed to measure the early effects of abaloparatide on tissue-based bone formation and resorption variables based on samples obtained by iliac crest bone biopsy after fluorochrome labeling. The study will consist of a Screening Period (up to 1 month), a Pretreatment Period (approximately 1 month), a Treatment Period (3 months), and a Month 4 visit one month after the last dose of study medication.

There is a sub study at one site to collect pQCT data and extend an additional 3 months of study drug administration for a total of 6 months of treatment.

The study design is presented in **Figure 1**. Full details of the protocol required assessments can be found in the Schedule of Assessments and Procedures (**Table 1**).

Figure 1: BA058-05-020 Study Design, Including Schematic of Bone Biopsy Labeling Procedure

**Table 1: Schedule of Assessments**

Procedure	Visit 1	Visit 2 (±4 days)	Visit 3 (+4 days)	Visit 4 (±4 days)	Visit 5 (±4 days)	Visit 6 (±7 days)
	Screening (30 Days)	Pre-treatment	Day 1	Month 1	Month 3	Month 4
Informed consent	X					
Verification of entry criteria	X	X				
Review of medical history a	X	X	X	X	X	X
Physical examination b	X					
Symptom directed physical examination		X	X	X	X	X
Vital signs c	X	X	X	X	X	X
Weight and height measurements d	X		X	X	X	X
12-lead Electrocardiogram e	X		X		X	X
Urinalysis (dipstick) f	X		X	X	X	
Chemistry blood collection g	X		X	X	X	
Hematology blood collection	X		X	X	X	
Coagulation (Prothrombin time and PTT) blood collection	X				X	
PTH (1-84)	X				X	
25-hydroxyvitamin D level	X					

Procedure	Visit 1	Visit 2 (±4 days)	Visit 3 (+4 days)	Visit 4 (±4 days)	Visit 5 (±4 days)	Visit 6 (±7 days)
	Screening (30 Days)	Pre-treatment	Day 1	Month 1	Month 3	Month 4
1,25-dihydroxy vitamin D level	X					
FSH	X					
Thyroid stimulating hormone	X					
Injection training for subjects		X				
Dispense calcium and vitamin D supplements n	X	X	X	X		
Study medication (abaloparatide) administration			Daily abaloparatide administration until and including the day of bone biopsy			
Demeclocycline (dispense and administration)		X h				
Tetracycline (dispense and administration)				X i		
Transiliac crest bone biopsy j					X	
Serum markers of bone metabolism (PINP and CTX)			X	X	X	
AP and lateral lumbar and thoracic spine radiographs	X					
Clinical assessment of new fractures k		X	X	X	X	X
Collect blood for immunogenicity testing			X		X	
BMD of lumbar spine, total hip, and femoral neck	X				X	

Procedure	Visit 1	Visit 2 (±4 days)	Visit 3 (+4 days)	Visit 4 (±4 days)	Visit 5 (±4 days)	Visit 6 (±7 days)
	Screening (30 Days)	Pre-treatment	Day 1	Month 1	Month 3	Month 4
Investigator assessment of local tolerance (dermal reactions assessment)			X	X	X	
Subject diary review 			X	X	X	
Document AEs and concomitant medications m	At any time, question subject at each visit					
Drug supply/resupply/accountability		X	X	X	X	

a Including alcohol and tobacco use assessment.

**Error! Reference source not found.** A complete physical examination includes a review of the following systems: head/neck/thyroid, eyes/ears/nose/throat, respiratory, cardiovascular, lymph nodes, abdomen, skin, musculoskeletal, and neurological. Breast, anorectal, and genital examinations will be performed when medically indicated. After screening, any clinically significant abnormal findings in physical examinations not present at screening should be reported as AEs.

**Error! Reference source not found.** Vital signs include blood pressure (systolic and diastolic), temperature (oral), pulse rate, and respiratory rate. These will be assessed following a 5-minute rest (seated or supine) and before blood sample collection. At visits when study drug is administered at the site, vital sign assessments will be collected before the dose of study drug. Only blood pressure, pulse rate, and respiration rate are to be recorded one hour post-dose. Supine and standing blood pressure measurements will be performed at each visit during the Treatment Period.

**Error! Reference source not found.** Height is to be measured in the standing position with shoes off using a medical stadiometer.

**Error! Reference source not found.** An ECG will be recorded immediately prior to dosing and one hour post-dose during the Treatment Period.

**Error! Reference source not found.** All routine urinalysis will be performed on a sample freshly voided during the visit and sent to a central lab for microscopy if test is positive for micro-organisms via dipstick.

**Error! Reference source not found.** Serum chemistry will be measured predose at Visits 3, 4, and 5.

**Error! Reference source not found.** Eighteen days before Day 1 of the Treatment Period (Visit 3), subjects who remain eligible for study participation will begin the first bone biopsy labeling procedure with administration of 150 mg demeclocycline 4 times daily for 3 days followed by a 12-day intermission, and then demeclocycline for 3 additional days at the same dose.

**Error! Reference source not found.** Approximately 23 to 26 days before Month 3 (Visit 5), subjects will begin the second bone biopsy labeling procedure with administration of 250 mg tetracycline 4 times daily for 3 days followed by a 12-day intermission, and then tetracycline for 3 additional days at the same dose.

**Error! Reference source not found.** Transiliac crest bone biopsy 5-8 days after last tetracycline dose. Sponsor Medical Monitor will decide if included in Early Termination Visit.

**Error! Reference source not found.** If the subject reports that a fracture has occurred, remind the subject to bring X-rays and any medical reports of the fracture to the next clinic visit. Documentation must be obtained on all new fractures that occur during the study. This documentation should be maintained in the source documents.

- l Subject will be instructed on completion of diary in the Pretreatment Period to include administration of medications for bone biopsy labeling procedure. The subject medication diary will be reviewed by study personnel at each study visit during the Treatment Period to ensure subject compliance.
- m AEs and SAEs will be recorded on the case report forms starting from the time of subject entry into the Screening Period (Visit 1) of the study (signed informed consent) until 30 days after the last dose of study medication. All AEs will be followed until resolution or stabilization. Any SAEs that occur at any time after completion of the study, which are considered by the Investigator to be related to study treatment, must be reported to the Sponsor or its designee.
- n Vitamin D supplements are required to be administered daily from the Pretreatment Period until the end of the Treatment Period. Calcium will also be administered daily, with the exception of the days of administration of demeclocycline and tetracycline where calcium administration will be withheld.

### 1.2.2 Randomization Methodology

This is a single arm study, and randomization is not used. i.e., not applicable.

### 1.2.3 Unblinding

This is an open-label study, and there is no blinding of study medication. i.e., not applicable.

### 1.2.4 Study Procedures

The schedule of assessments, as outlined in the study protocol, is provided in [Table 1](#).

### 1.2.5 Study Endpoints

- Change from baseline to 3 months in dynamic indices of bone formation in the relevant bone envelopes (cancellous, endocortical, intracortical, and periosteal)
  - Mineralizing surface (MS/BS)
  - Mineral apposition rate (MAR)
  - Bone formation rate (BFR/BS)
- Structural indices in the intracortical envelope at Month 3
  - Cortical porosity (Ct.Po/Ct.Ar)
- Static indices in the relevant bone envelopes (cancellous, endocortical, intracortical, and periosteal) at Month 3
  - Osteoid volume (OV/BV)
  - Osteoid surface (OS/BS)
  - Osteoid thickness (O.Th)
  - Wall thickness (W.Th)
  - Eroded surface (ES/BS)
- Change from baseline to 3 months in special histomorphometric variables in the relevant bone envelopes (cancellous, endocortical, intracortical, and periosteal)
  - Remodeling, modeling, and overflow modeling-based formation (RmF/BS, MF/BS, oMF/BS)
- Change in serum procollagen type I N-terminal propeptide (s-PINP) and carboxy-terminal cross-linking telopeptide of type I collagen (s-CTX) from baseline to 1 and 3 months
- Correlations of tissue-based indices of bone formation and bone resorption with s-PINP and s-CTX
- Overall safety and tolerability of abaloparatide in postmenopausal women with osteoporosis.

## **2 SUBJECT ANALYSIS POPULATIONS**

### **2.1 Population Definitions**

The primary population for all efficacy analyses will be the Bone-Biopsy Population, which is defined as all enrolled subjects who received an evaluable biopsy, defined as a biopsy sample that can be analyzed in the laboratory. The primary population for all safety analyses will be the Safety Population, which will be defined as all enrolled subjects who received at least one dose of abaloparatide.

### **2.2 Protocol Deviations**

As documented in the BA058-05-020 Medical Monitoring Plan, the definitions/classifications of protocol deviations are as defined in [REDACTED] document CTM002-SOP (Managing Protocol Deviations; Effective Date: 05 Sep 2017). A protocol deviation is any intentional, unintentional change or non-compliance with the current IRB/IEC and Competent Authority approved protocol procedures or requirements per ICH/GCP guidelines. A deviation may result from the action or inaction of the subject, Investigator or site staff.

Subjects with protocol deviations will be identified and recorded by the clinical trial vendor [REDACTED] using their Clinical Trial Management System (CTMS). The list of protocol deviations and protocol violations will be reviewed by the clinical team on a regular basis throughout the study. At the end of the study, a list of the protocol deviations/violations will be generated from the CTMS and included in the clinical study report (CSR).

## **3 GENERAL STATISTICAL METHODS**

### **3.1 Sample Size Planned and Specified in the Protocol**

In the AVA study of teriparatide and denosumab (Dempster, 2016), the mean ( $\pm$  SD) change from baseline in cancellous MS/BS (%) for teriparatide was 13.90 ( $\pm$  9.38) at 3 months. In the ACTIVE study, the median % change from baseline in s-PINP at 3 months was 60% for abaloparatide and 94% for teriparatide. The ratio between the 2 groups is approximately 2/3 (= 60%/94%).

Using the same ratio and the results for teriparatide obtained from the AVA study, we can assume that the mean change from baseline in cancellous MS/BS (%) for abaloparatide at 3 months will be 9.2% (= 13.90\*2/3). Assuming a standard deviation (SD) of 12.0%, a sample size of 21 completers will provide at least 90% power to detect a statistically significant change from baseline in cancellous MS/BS (%) for abaloparatide at 3 months of 9.2%. The study is planned to enroll approximately 25 subjects to accommodate a drop-out rate of 15%, including those with non-evaluable bone biopsy. Additional subjects may be enrolled if the number of evaluable biopsies is insufficient to achieve this power.

### **3.2 General Methods**

Continuous variables will be summarized with the following descriptive statistics: number of observations, (arithmetic) mean, standard deviation (SD), median, interquartile range (Q1 and Q3), minimum, and maximum. If the number of subjects is 1, the standard deviation will be left blank. Categorical data will be summarized with frequencies for each category and corresponding percentages.

All data listings that contain an evaluation date will contain a relative study day. Screening, pre-treatment and on-treatment study days are numbered relative to the day of the first dose of study medication which is designated as Day 1. The preceding day is Day -1, the day before that is Day -2, etc.

In listings, data will be presented with the same precision as the original data. Derived data may be rounded to 1 decimal place greater than the original data for presentation purposes.

Frequency percentages will be presented with 1 decimal.

For all summaries, the mean and median will be presented to 1 decimal place greater than the original data, standard deviation (SD) to 2 greater than the original data, and the minimum and maximum will be presented to the same number of decimal places as the original data.

The summaries will include:

- data from subjects participating in the main study (i.e., subjects with planned treatment duration of 3 months, plus 1 month after the last dose of study medication); and
- data up to Month 4 for subjects participating in the sub-study (i.e., subjects with planned treatment duration of 6 months, plus 1 month after the last dose of study medication).

All subject data (from the main study and the sub-study) will be presented in listings.

### **3.3 Computing Environment**

All descriptive and statistical analyses will be performed using SAS statistical software Version 9.4, or later version. Medical history and AEs will be coded using the Medical Dictionary for Regulatory Activities (MedDRA), Version 21.0. Concomitant medications will be coded using the World Health Organization Drug Dictionary (WHODrug Global March 2018 B3).

### **3.4 Baseline Definitions**

Unless otherwise specified, the baseline value is defined as the last value obtained prior to the first dose of study medication.

### **3.5 Data Pooling**

Data from all sites will be pooled together for all analyses unless otherwise specified.

### **3.6 Adjustments for Covariates**

No adjustment for covariates will be made in any of the planned analyses for study endpoints.

### **3.7 Multiple Comparisons**

Not applicable.

### **3.8 Subgroups**

Not applicable.

### **3.9 Withdrawals, Dropouts, Loss to Follow-up**

Data from subjects who do not complete the study, or who are lost to follow-up will be included in data listings and in summary tables, as appropriate.

### **3.10 Missing, Unused, and Spurious Data**

Unless otherwise specified, there will be no imputation of data.

In the event that incorrect data are discovered after database lock, the impact of such incorrect data will be assessed and a determination will be made as to whether the data need to be corrected in the database (and subsequently in the analysis). In cases where it is decided that the data need to be corrected, the decision will be documented and the documentation will be saved in the Trial Master File.

All available data will be included in data listings.

### **3.11 Visit Windows**

Unless otherwise specified, data will not be analyzed using visit windows; instead, the nominal visit will be used.

### **3.12 Interim Analyses**

There are no interim analyses planned for this study.

## **4 STUDY ANALYSES**

Unless otherwise specified, all summary tables described in this section will be presented for the Safety Population.

### **4.1 Subject Disposition**

Subject disposition will include the number of subjects enrolled, included in the safety population and reasons for exclusion from the safety population, included in the bone-biopsy population and reasons for exclusion from the bone-biopsy population, completed treatment, discontinued treatment with reasons for treatment discontinuation, completed the study, discontinued study with primary reasons for not completing the study.

A by-subject data listing of treatment completion and study completion information, including the primary reasons for treatment discontinuation and for study withdrawal, as recorded in the eCRF, will be presented.

## **4.2 Demographics and Baseline Characteristics**

Demographic and baseline characteristics will be summarized. Age, height, weight, body mass index (BMI), total hip T-score, total hip BMD, femoral neck T-score, femoral neck BMD, lumbar spine T-score, and lumbar spine BMD will be summarized using descriptive statistics (number of subjects, mean, SD, median, interquartile range, minimum and maximum). The number and percentage of subjects in each age (<65 years, 65 to <75, >=75), gender, ethnicity, race and total hip/lumbar spine/femoral neck T-score category (> -2.5 to <= -2.0; > -3.0 to <= -2.5; and <= -3.0) will also be presented.

The number and percentage of subjects in each substance use category (tobacco history, alcohol use, use of other substances) and with prevalent clinical fracture will also be presented.

Medical history will be presented by MedDRA system organ class (SOC) and preferred term (PT) summarizing the proportion of subjects who have a condition noted.

All subject data collected for demographics and baseline characteristics will be presented in data listings.

## **4.3 Extent of Exposure and Compliance**

Study drug exposure and compliance will be calculated using the data recorded on the Visit Day Study Medication Injection, the Injected Medication Accountability Log, and the End of Treatment eCRF pages as follows:

- Duration of Exposure (days)  
= date of last study medication – date of first study medication + 1  
Note: The date of last study medication will be obtained from the End of Treatment eCRF. If the date of last study medication is missing, the last available date of study medication on the Visit Day Study Medication Injection eCRF will be used.
- Number of Doses Delivered  
= duration of exposure - number of missed doses per subject diary
- Compliance (%)  
= (Number of doses delivered / Duration of exposure) x 100%

For demeclocycline and tetracycline, the number of doses delivered will be calculated as

- Number of Tablets Dispensed - Number of Tablets Returned.

Descriptive statistics (number of subjects, mean, SD, median, interquartile range, minimum and maximum) will be used to summarize duration of exposure, number of doses delivered, and compliance.

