6.5. Treatment Compliance

To ensure treatment compliance, the Investigator or designee will supervise all study drug administration that occurs at the site. At each study visit, the Investigator or designee will review subject compliance with study drug administration and remind the subject of study drug dosing requirements. Subject compliance will be ascertained by two methods: subject diaries and measuring residual drug in the cartridge.

Discrepancies between expected and actual dosing will be assessed and discussed with the subject. All discrepancies, causes and subject retraining will be documented in the medical charts, and recorded in the eCRF as appropriate. If a subject does not take all study medication (abaloparatide) as required, the reason for the missed dose is to be discussed with the subject during the visit.

Although calcium and vitamin D are considered concomitant medications for this study, missed doses of calcium and vitamin D will be determined by performing a pill count. If a subject demonstrates continued noncompliance with required abaloparatide dosing despite educational efforts, the Investigator should contact the Sponsor Medical Monitor to discuss discontinuation of the subject from the Study.

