7.2. Study Schedule

This study is comprised of six clinic visits. Study assessments are to be performed according to the Schedule of Events ([Table 1](#)). There is a \pm 4-day window for each clinic visit, other than the Day 1 for which there is a +4-day window and Month 4 visit for which there is a \pm 7-day window.

The study will consist of a Screening Period (up to 1 month), a Pretreatment Period (approximately 1 month), a Treatment Period (3 months), and a Month 4 Visit (one month). During the Treatment Period, subjects will have clinic visits for study-related protocol procedures at Day 1, Month 1, and Month 3. For the purpose of this study, one month is equal to 30 days.

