#### **4.4 Concomitant Medication**

Concomitant medications will be coded using the WHO Drug Dictionary. The number (and percentage) of subjects taking medications will be tabulated by Anatomical Therapeutic Chemical (ATC) class and preferred term (PT).

The tabulations will include concomitant medications taken from the date of the first dose of study medication (Day 1) until 30 days after the last dose of study medication. Medications that did not end prior to the first dose of study medication will be included in the summary.

Prior medications (those with start date prior to the first dose of study medication) will also be summarized by ATC and PT.

All recorded prior and concomitant medications will be presented in a by-subject listing.

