### **4.7.1 Adverse Events**

Analyses of AEs will be performed for those events that are considered to be treatment-emergent adverse events (TEAEs). A TEAE is defined as any AE that was absent (i.e., had not occurred) prior to the start of study drug and which occurs on or after the date of the first dose of study drug and within 30 days of the last dose of study drug, or any AE that started during the study period(s) prior to the start of study drug and worsened in severity after the start of study drug within 30 days of the last dose of study drug.

In any tabulation of adverse events, a subject contributes only once to the count for a given SOC or PT. For summaries by severity, a subject with multiple occurrences of an AE will be represented under the most severe occurrence. For summaries by relationship to study drug, a subject with multiple occurrences of an AE will be represented under the most related occurrence.

The number (%) of subjects with TEAEs will be summarized by SOC and PT. This analysis will also be performed for the following types of AEs: most common ( $\geq 5\%$ ) TEAEs, severe TEAEs, serious TEAEs (SAEs), TEAEs leading to study drug withdrawal, drug-related TEAEs (with probable or possible relationship to study drug), and AEs that are not treatment-emergent.

The number (%) of subjects with TEAEs will also be summarized by PT in order of decreasing frequency.

The number (%) of subjects with TEAEs by SOC and PT will also be tabulated by maximum severity (mild, moderate, or severe). A similar tabulation will be presented by relationship (related or not related) to study drug.

Subject listings will be provided for all AEs by SOC and PT. Listings will also be produced for AEs with outcome of deaths, severe AEs, SAEs, and AEs leading to study drug withdrawal.

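### When the last-dose date is missing, SAP 4.3 substitutes the last clinic injection, which can understate exposure by up to about 60 days, and SAP 4.4 and 4.7.1 do not say which date closes their 30-day windows

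*SAP*

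**What the plan says.** SAP 4.3 defines duration of exposure as "date of last study medication – date of first study medication + 1". On the end date it says: "The date of last study medication will be obtained from the End of Treatment eCRF". If that entry is blank, "the last available date of study medication on the Visit Day Study Medication Injection eCRF will be used". The number of doses delivered is then "duration of exposure - number of missed doses per subject diary", and compliance is doses delivered divided by duration.

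Two other sections depend on a last-dose date. SAP 4.7.1 counts an event as treatment-emergent if it occurs after the first dose and "within 30 days of the last dose of study drug". SAP 4.4 tabulates concomitant medication "until 30 days after the last dose of study medication". Neither refers to 4.3. SAP 3.10 allows no imputation unless otherwise specified.

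On dosing, Protocol 6.4 has subjects inject themselves once a day, with the dose taken in clinic on visit days. Protocol 7.2 states that during treatment "subjects will have clinic visits for study-related protocol procedures at Day 1, Month 1, and Month 3". Protocol 6.5 adds: "Subject compliance will be ascertained by two methods: subject diaries and measuring residual drug in the cartridge".

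**The concern.** The visit-day form records injections given at clinic visits. With daily home dosing and no visit between Month 1 and Month 3, its last entry is the last attended visit and not necessarily the last dose. The plan collects other evidence of later dosing (diary, accountability log, residual drug), and SAP 4.3 itself names the accountability log as a data source, but the fallback uses none of it.

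Three things are at stake:

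- **Exposure.** The duration is cut back to the last clinic visit, and the error runs only toward understatement.
- **Compliance.** SAP 4.3 does not limit the diary's missed doses to the shortened period. Missed doses from the whole period can be subtracted from a truncated duration.
- **Event and medication windows.** SAP 4.3 is the only place where the SAP derives a last-dose date. If it is carried into 4.7.1 and 4.4, the windows can close while the subject is still injecting. If it is not, those windows have no defined end for such a subject.

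**Working it through.** The documents give no figure for this gap, so there is none to reproduce. The check is date arithmetic on the visit schedule.

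**Inputs.** One month is 30 days, and the Month 1 and Month 3 visits have ±4-day windows (Protocol 7.2). Dosing is daily (Protocol 6.4). Month 1 is taken as Day 30 and Month 3 as Day 90. With the first dose on Day 1, exposure in days equals the day number of the last dose.

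**Formulas.**
- Gap = true last-dose day − last clinic injection day.
- Substituted window end = last clinic injection day + 30.
- On-drug days outside the window = true last-dose day − substituted window end, or 0 if negative.

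**Last clinic injection at Month 1, home dosing up to the Month 3 visit that is not recorded.**

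| Case | Clinic day | True last dose | Gap | Exposure understated | Window ends | On-drug days outside |
|---|---|---|---|---|---|---|
| Nominal, day before Month 3 | 30 | 89 | 59 | 59/89 = 66.3% | Day 60 | 29 |
| Nominal, on the Month 3 day | 30 | 90 | 60 | 60/90 = 66.7% | Day 60 | 30 |
| Widest windows, on the Month 3 day | 26 | 94 | 68 | 68/94 = 72.3% | Day 56 | 38 |
| Narrowest windows, day before Month 3 | 34 | 85 | 51 | 51/85 = 60.0% | Day 64 | 21 |

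Placing Month 1 at Day 31 and Month 3 at Day 91 leaves the gaps unchanged and puts the percentage between about 59% and 72%. In the first row, the true window would run to Day 89 + 30 = Day 119.

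**Last clinic injection on Day 1, home dosing up to Month 1.** The true last dose is Day 29, so exposure is recorded as 1 day instead of 29 (gap 28). The substituted window ends on Day 31, so no on-drug day falls outside it nominally. At the latest visit date and under either day convention, at most 3 do.

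**Month 3/Early Termination injection recorded.** Protocol 7.2.10 has the last dose given in clinic, so the gap is about 0.

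**Compliance, illustration with assumed figures.** Take 6 missed doses over 89 days, all in a recovered diary. True compliance is (89 − 6)/89 = 93.3%. Against the Month 1 fallback it is (30 − 6)/30 = 80.0%. With no missed doses, both are 100%.

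**Effect on summaries, per affected subject, if 25 are treated.** A 59-day shortfall lowers mean exposure by 59/25 = 2.4 days. If an event is reclassified, the rate for that term moves by 1/25 = 4 percentage points.

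**Sub-study.** The Month 4 to Month 6 interval has the same 60-day spacing, but SAP 3.2 limits the summaries to data up to Month 4.

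**The case against.** The strongest reply is that the fallback is second-line and will seldom matter. The End of Treatment page comes first, and missing data are queried (Protocol 10.7). Subjects who withdraw are encouraged to attend Month 3/Early Termination (Protocol 5.3.2 and 7.8), where the gap is about zero. Non-attenders are pursued (Protocol 7.8 and 8.3), and a contact that yields an adverse event can also yield a last-dose date. Diaries are reviewed and pens returned at visits, so a subject lost between visits has often returned neither. Exposure to the last documented dose is then a defensible minimum. Safety analyses are descriptive, and no efficacy analysis uses this date.

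Most of this stands and limits the size of the point. It does not answer the case where later dosing is documented and the rule still sets it aside. Nor does it fill the gap in 4.4 and 4.7.1.

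A reader might infer that the SAP excludes on-drug events from the treatment-emergent tables. The documents do not go that far:

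- The note belongs to the exposure calculation, and 4.7.1 and 4.4 do not adopt it.
- If it is carried over, the loss needs a missing date, a last clinic injection at Month 1, dosing past about Day 60 and an event after that.
- SAP 4.7.1 still lists such events and tabulates them as not treatment-emergent, though in the same table as events from before the first dose.

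A reader might also take the 15% drop-out allowance (about 4 of 25) as the number affected, or assume that missing dates mark subjects who stopped for tolerability. The 15% covers all drop-outs and non-evaluable biopsies and does not estimate missing last-dose dates. Nothing in the documents supports the second idea, and a subject who stopped soon after a visit would have a fallback close to the truth.

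**Conclusion.** The point holds at minor severity. Followed as written, SAP 4.3 can understate exposure by up to about 60 days in a main-study subject whose End of Treatment date is missing and who has no Month 3/Early Termination injection. It can also distort compliance, because missed doses are not limited to the shortened period.

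The effect on treatment-emergent events is conditional. SAP 4.4 and 4.7.1 leave open which date applies. If the 4.3 date is used, about 29 on-drug days can fall outside the window nominally after a Month 1 fallback, and none nominally after a Day 1 fallback.

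These sizes are worst cases that assume daily injection up to the Month 3 visit. The documents do not give the number of affected subjects, which may be zero. If every last-dose date is recorded, there is no effect. If neither diary, pens nor contact information is recovered, no rule can restore the true date.

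**What to change.** In SAP 4.3, replace the fallback note with wording to this effect: if the End of Treatment date is missing, use the latest dose date documented in any collected source (diary, accountability log, documented contact or visit-day form). Count missed doses only up to that date. If only the clinic injection is available, report exposure to it and flag the value as a minimum.

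In SAP 4.4 and 4.7.1, refer to that date. Add to 4.7.1 that when the true last-dose date is unknown, a recorded event after the first dose is not classed as non-treatment-emergent solely because of the substituted date.

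It is better not to assume a window date such as the earlier of scheduled end of treatment and study discontinuation. Under Protocol 8.3 a subject is not formally lost until her scheduled end-of-study visit would have occurred. Such a rule could therefore add many off-drug days for someone who stopped early.

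The cost is a few lines of SAP text and one derived date with a flag. The downside is that some off-drug events in these subjects may be counted as treatment-emergent, so they should be marked in the listing.
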